13.1 Source Data

Source data are defined as all information in original records and certified copies of original records of clinical findings, observations or other activities in a clinical study necessary for the reconstruction and evaluation of the study. Source data are contained in source documents.

13.2 Source Documents

Source documents are defined as original documents, data and records (e.g. hospital records, clinical and office charts, electronic patient records, laboratory notes, memoranda, patient diaries or evaluation check lists, pharmacy dispensing records, recorded data from automated instruments, copies or transcriptions, microfiches, photographic negatives, microfilm or magnetic media, x-rays, patient files, records kept at pharmacy, at the laboratories and at medico technical departments) involved in this clinical study.

In case of data that are result of patient reporting and will not be documented in clinical routine, the e-CRF is the source document, if the patients answer is documented there without prior documentation.

13.3 Direct Access

Direct access is defined as the permission to examine, analyse, verify and reproduce any records and reports that are important for evaluation of a clinical study. Any party with direct access should take all reasonable precautions within the constraints of the applicable regulatory requirements to maintain the confidentiality of patient identities and sponsor proprietary information.

The investigator agrees that representatives or the designees of the sponsor such as monitors and auditors, and appropriate regulatory agencies will be given direct access to the regular clinical files of the patient.

14. Quality Control and Quality Assurance

14.1 Quality Control

Quality control is defined as the operational techniques and activities, such as monitoring, undertaken within the quality assurance system to verify that the requirements for quality of the study related activities have been fulfilled. Quality control should be applied to each stage of data handling to ensure that all data are reliable and have been processed correctly.

14.2 Initiation Visit

At each site an initiation visit will be performed by a representative of the CRO before enrolment of the first patient at this site.

14.3 Study Monitoring

The investigators and study sites involved in the clinical trial are obliged by current regulations and by contract to permit clinical trial-related monitoring, audits and regulatory inspections, if applicable, including provision of direct access to source data and documents.

A Risk Based Monitoring Plan (RBMP) will establish the guidelines for conducting quality management (e. g. on-site monitoring visits, off-site central monitoring, and other tasks of quality control). The RBMP will identify the requirement to perform an ongoing review of any e-CRF item (automated, by means of statistics and by research professionals, e. g. manual queries), the amount of source data verification and review, the frequency of on-site monitoring visits and actions to be taken based on the result of central and on-site monitoring. Thus, frequency of on-site visits and amount of source data verification is dynamic and dependent on performance and quality of each study site. Authorised, qualified representatives of the designated CRO will accomplish the monitoring of the study sites during the trial.

It is important that the investigator and relevant personnel are available during the monitoring visits and that an appropriate location and sufficient amount of time is devoted to the process. During the monitoring visit a PC with internet connection should be available to the monitor for direct connection to the internet database of the study and to all the data of the patients if stored in the data system of the hospital.

The main duty of the monitor is to help the sponsor and the investigator to maintain a high level of ethical, scientific, technical and regulatory quality in all aspects of the trial. At regular intervals during the study, the local site will be contacted through monitoring visits, letters/ emails or telephone calls by a monitor to review the progress of the study.

14.4 Close Out Visit

Independent close-out visits are not planned. The sponsor is responsible for return of IP devices and related equipment from participating study sites. In case of special requests by the sponsor, a separate close out visit may be performed at the end of the trial participation of a study site. The close out visit may be combined with the last monitoring visit.

14.5 Quality Assurance

Quality Assurance is defined as the planned and systematic actions that are established to ensure that the study is performed and the data are generated, documented (recorded) and reported in compliance with Good Clinical Practice (GCP) as defined in ISO 14155 and the applicable regulatory requirements.

The investigator should permit auditing by or on behalf of the sponsor and inspection by applicable regulatory authorities. The investigator shall take appropriate measures required by the sponsor to take corrective actions for all problems found during the audit or inspections.

14.5.1 Inspections

An Inspection is defined as the act by a regulatory authority of conducting an official review of documents, facilities, records and any other resources that are deemed by the authorities to be related to the clinical study and that may be located at the site of the study, or at the sponsors and/or clinical research organisation facilities or at any other establishments deemed appropriate by the regulatory authorities.

14.5.2 Audits

An audit is a systematic and independent review of study related activities and documents to determine whether the validated study related activities were conducted and the data were recorded, analysed and accurately reported according to the protocol, designated Standard Operating Procedures (SOPs), GCP as defined in ISO 14155:2020 and the applicable regulatory requirements. An independent audit at the study site may take place at any time during or after the study.

15. Ethical and Legal Consideration

This is a trial with a non-marketed diagnostic medical product as IP which meets relevant ethical and regulatory standards (e.g. EU MDR, related national acts, GCP as defined in ISO 14155:2020). The trial will be conducted in accordance with the principles laid down in the Declaration of Helsinki in its version of October 2013 (Fortaleza) (Appendix V).

Before initiating the study, approval of the corresponding Ethics Committees will be obtained.

15.1 Ethical Consideration

15.1.1 Ethics Committee (EC)

Provided this is not contradictory to national law, the principal investigator is responsible for submitting an application to the appropriate EC. Furthermore, the principal investigator is required to forward to the sponsor or the CRO a copy of the written and dated approval or favourable opinion of the local EC. The CRO will provide substantial support for any EC submission. The sponsor is responsible to assure that approval of the local EC is obtained prior to study start in the respective study site in accordance with local requirements.

During the trial, any modification to trial application or substantial amendment to clinical trial protocol should be submitted to regulatory bodies and ECs involved. They will also be informed of any event likely to affect the safety of patients or the continued conduct of the trial, in particular of any change in safety aspects.

15.1.2 Steering Committee (SC)

The trial SC will consist of a small group of medical experts (representatives of study sites and independent experts) and an expert biostatistician (refer to Appendix I). The functions of the SC are the following:

- Overall responsibility for the execution and scientific reporting of the trial.
- Advice on the scientific and clinical aspects of the study protocol and related documents.
- Together with the sponsor responsibility for the conduct of the study according to the guidelines of GCP as defined in ISO 14155:2020 and applicable medical guidelines including the monitoring of patient recruitment.
- Reassessment of benefit-risk ratio if deemed necessary.
- Decisions on continuation or termination of the study.

A SC charter providing operating procedures and responsibilities will be discussed and enacted at the latest during the second meeting. Meeting frequency will be defined by the committee and may vary depending on tasks. Meetings may be conference calls or face-to-face meetings. Minutes of each meeting will be provided.

15.1.3 Endpoint Review Committee (ERC)

The ERC will consist of clinical experts and will centrally adjudicate SAEs as primary and secondary outcome parameters if based on clinical events. Adjudication will primarily be performed as a continuous onlineprocess within the e-TMS, depending on the number of documented and cleaned SAEs. In addition, meetings may be performed, either face-to-face or conference calls, if needed. Minutes of each meeting will be provided.

An ERC charter providing operating procedures and responsibilities will be discussed and enacted latest at the ERC kick-off meeting prior to start of adjudication.

15.1.4 Data and Safety Monitoring Board (DSMB)

This diagnostic accuracy study (stage 1) has no pre-defined treatment and no blinded therapies. The primary outcome parameter is sensitivity and specificity of detection of clinically relevant hemorrhage within 48 hours following thyroid surgery. The IP is only of diagnostic character. One component of the IP (the catheter-based pressure sensor) will be inserted into the surgical wound before closure but no blinding of the procedures is performed. Thus, the function of a DSMB with access to unblinded data necessary for assessment of the safety status of a blinded therapy study can be ensured in the context of this diagnostic study without blinded therapies by ERC and SC.

15.2 Legal Consideration

The study will be performed in Germany and Austria as medical device study with a diagnostic IP in accordance with EU MDR and related national acts as well as ISO 14155:2020 and EU General Data Protection Regulation (2016/679, GDPR).

In general, no therapy procedures will be defined by the study protocol with the exception of the index thyroid surgery. Thyroid surgery procedures for the individual study patient will be decided and performed by the treating physician in line with applicable medical guidelines and local policies in routine clinical care based on the clinical situation of the individual study patient.

All other medical therapies applied within this trial are at the discretion of the treating physician and will be utilised as routine clinical care therapies with marketed products used in line with their corresponding market authorisation and represent SOC as defined in current medical guidelines. This also applies to all medical procedures within the trial.

No additional invasive or stressful diagnostic or therapeutic procedures will be performed compared to routine clinical care of the patient population in focus.

Approval of the study from regulatory authorities and ethics committees will be obtained before first patient in.

15.3 Modification of Protocol

Any substantial amendment to the clinical trial protocol requires written approval/favourable opinion by responsible regulatory bodies and ECs prior to its implementation, unless there are overriding safety reasons that require immediate action. In some instances, an amendment may require a change to the informed consent form. In this case, the investigator must receive approval/favourable opinion of the responsible EC concerning the revised informed consent form prior to implementation of the change.

15.4 Financing and Insurance

The trial is completely funded by the sponsor. The costs necessary to perform the study will be agreed upon with each investigator and will be documented in a separate financial agreement which will be signed by the investigator and the CRO on behalf of the sponsor, prior to the study commencing.

A patient insurance within this study on top of insurance in place by treating institutions and manufacturers of medical devices used within this study according to routine clinical has been effected.

15.5 Investigators' Information on investigational medical product

Investigators will be informed and trained on the diagnostic IP and its use within the index thyroid surgery by the sponsor. Each training will be certified. In general, other medical therapies and medical procedures are not affected by the diagnostic IP.

In case of new information related to the diagnostic IP or its handling gathered within the course of the study the sponsor is responsible for timely information of the investigators and the patients, if necessary.

15.6 Personal Data and Data Protection

All data obtained in the context of the clinical trial are subject to data protection. This applies to patients' data as well as to investigators' personal data which may be included in any database of the sponsor or the CRO. Data protection processes and responsibilities according to EU General Data Protection Regulation (GDPR) are defined in an agreement on joint control of data between study sites and the sponsor as well as in an agreement of contract data processing between the sponsor and the CRO.

The study sites are responsible that patient documents (e.g. copies of reports on special findings) transmitted to the CRO or the sponsor contain no names or other directly identifying data, but only the year of birth and a relevant patient study number given by the e-TMS. The storage of data for statistical analysis shall likewise be performed only under the patient's study number.

15.7 Data Handling and Record Keeping

15.7.1 Completion of Case Report Forms

All medical data in this trial are to be recorded directly in e-CRFs provided by the CRO. Documentation on paper will be restricted to exceptional circumstances, only, which have to be approved in writing by the CRO. The investigator must ensure the accuracy, completeness and timeliness (and legibility in case of documentation on paper) of data.

15.7.2 Archiving

The principal investigator must maintain confidential all study documentation, and take measures to prevent accidental or premature destruction of these documents. The principal investigator has to retain the study documents (i.e. investigator site file) after the completion or discontinuation of the study for the time period as required by national legislation. This especially applies to patient's signed informed consent forms and the patient identification list.

The principal investigator must notify the sponsor prior to destroying any essential study documents within the specified period following completion or discontinuation of the trial.

15.8 Confidentiality

All information disclosed or provided by the sponsor (or any company / institution acting on his behalf), or produced during the trial, including, but not limited to, the clinical trial protocol, the e-CRFs and the results obtained during the course of the trial, is confidential. The principal investigator or any person under his/her authority agrees to undertake to keep confidential and not to disclose the information to any third party without the prior written approval of the sponsor. The investigators shall be bound by the same obligation as the principal investigator. The principal investigator shall inform the investigators of the confidential nature of the trial. Both, the principal investigator and the investigators shall use the information solely for the purposes of the trial, to the exclusion of any use for their own or for a third party's account.

15.9 Responsibilities

The sponsor of this trial is responsible for taking all reasonable steps to ensure the proper conduct of the trial with regard to ethical aspects, clinical trial protocol compliance, integrity and validity of the data recording.

16. Final Report and Publication Policy, Property Rights

The sponsor will be responsible for preparing the final study report that is to be signed by the SC. The sponsor will communicate the results of the trial to the investigators as well as to responsible regulatory bodies and ECs. The SC will be primarily responsible for the creation, review and submission of publications and presentations relating to the major aspects of the study within a timely fashion after completion of the study. All analyses will be the responsibility of the SC. Manuscripts for publication will be drafted by members of the SC or other interested investigators. All manuscripts will be subject to coordinated submission and review prior to submission. Coordination will be done by SC.

All relevant measures for transparency of clinical trials, and especially the recommendations of the editors of the major medical journals, will be met. The publication rules are regulated separately and described in detail in a publication policy that is confirmed by the SC and the sponsor.

All information and documents provided by the sponsor or its representatives are and remain the sole property of the sponsor. The investigators shall not mention any information for any other intellectual property rights. All results, data, documents and inventions, which arise directly or indirectly from the trial in any form, shall be the immediate and exclusive property of the sponsor.

17. Definitions and Classification

17.1 Protocol Deviation

A protocol deviation is any change, divergence, or departure from the study design or procedures defined in the EC-approved protocol (acc. to ICH guideline E3 - questions and answers, 2012).

17.2 Important Protocol Deviation

Important protocol deviations are any protocol deviations that may significantly impact the completeness, accuracy, and/or of the study data or that may significantly affect a subject's rights, safety, or well-being. For example, important protocol deviations may include enrolling subjects in violation of key eligibility criteria designed to reliability ensure a specific subject population or failing to collect data necessary to interpret primary endpoints, as this may compromise the scientific value of the trial. Protocol violation and important protocol deviation are sometimes used interchangeably to refer to a significant departure from protocol requirements (acc. to ICH guideline E3 - questions and answers, 2012). Study-specific definitions of important protocol deviations may be given by the SC.

Patients with important protocol deviations will be excluded from the per-protocol analysis. Details are given in the SAP.

18. References

- 8. Doran H.E, Wisemann S.M., Palazzo F.F et al. Post thyroidectomy bleeding:analysis of risk factors from a national registry, Br J Surg, https://doi.org/10.1093/bjs/znab015

Appendix II. Time Table

Section	Tasks	Date
Draft study planning	Draft Protocol	December 2020
Final study planning	Final protocol – First submission	February 2022
	Final protocol – Second submission	December 2022
Study preparation	E-TMS, e-CRF; other study relevant documentation	June 2021
	Start of site selection, site contacts, site evaluation	May 2021
	First EC submission	May 2021
	First submission to authorities	September 2021
	Second EC submission	October 2022
	Second submission to authorities	November 2022
Study initiation	Start of site contracting	August 2021
	Start of supply of sites with study materials, start of initiation visits	February 2022
	Start of recruitment period (FPI)	February 2023
	End of recruitment period (LPI)	January 2024
Study duration	End of follow-up of last patient	February 2024
	Median follow-up period of all patients	1 month
Database lock	End of final data cleaning	March 2024
Final analysis	Results to be presented to SC	April 2024

Appendix III. Patient questionnaires

Follow-up questionnaire on events

HEDOS-Studie: Patienten-Fragebogen zum Verlauf

Patienten ID: «PatientID», Geschlecht: «Geschlecht», Geburtsjahr: «Geb.Jahr» (Zentrums-ID «CID»)

Sehr geehrte Patientin, sehr geehrter Patient,

seit «Date_baseline» nehmen Sie als Patient(in) der Klinik/Praxis «Institution» («city») an der HEDOS-Studie teil, die Nachblutungen nach Schilddrüsen-Operationen mit einem neuen Diagnosegerät untersucht. Das Auftragsforschungsinstitut CRI in München wurde mit der Durchführung dieser Studie beauftragt.

Zu Beginn Ihrer Studienteilnahme wurden bereits Ihre medizinischen Daten durch Ihre Ärzte für diese Studie dokumentiert. Nun benötigen wir nach ihrer Schilddrüsen-Operation Informationen darüber, wie es Ihnen zur Zeit geht und wie es Ihnen zwischenzeitlich bezüglich Ihrer Gesundheit und auch Ihres Wohlbefindens ergangen ist. So ist es für die Auswertung der Studie auch wichtig zu erfahren, ob Sie seit Ihrer Entlassung nach der Schilddrüsen-Operation beim Arzt oder im Krankenhaus waren.

Wir bitten Sie daher, die folgenden drei Fragebögen vollständig auszufüllen und in dem beigefügten Rückumschlag an CRI in München zu schicken. Sie können den fertigen Rückumschlag ohne Briefmarke in einen Postbriefkasten ihrer Wahl einwerfen, denn das Porto bezahlt CRI.

WICHTIG: Aus Datenschutzgründen enthalten Ihre Fragebögen nur pseudonymisierte Daten, d.h. nur Ihre Patienten-Nummer im Rahmen der HEDOS-Studie sowie Ihr Geschlecht und Ihr Geburtsjahr. CRI kennt Ihren Namen und Ihre Anschrift nicht, daher haben Sie dieses Schreiben und die Fragebögen über Ihr Studienzentrum erhalten. Bitte notieren Sie aus diesem Grund auch keinen Namen auf den Fragebögen oder auf dem Briefumschlag und unterschreiben Sie bitte nicht.

Falls Ihnen Fragen unverständlich vorkommen oder Sie Schwierigkeiten beim Ausfüllen bzw. Fragen zur HEDOS-Studie haben, wenden Sie sich bitte an Ihr Studienzentrum. Die Telefonnummer finden Sie auf Ihrer Patienteninformation.

Wir bedanken uns sehr für Ihre Mithilfe!

Mit freundlichen Grüßen

Ihr HEDOS-Studienteam

.....

н	ED	os-st	udie: P	atienten-Fragebogen zum Verlauf	S	
Pa	tient	ten ID: «	PatientID»	, Geschlecht: «Geschlecht», Geburtsjahr: «Geb.Jahr» (Zentrums-ID «CID»)		
Fra	igeb	ogen v	om Patient	ten ausgefüllt am (Datum):/_/ (Tag / Monat / Jahr)		
1.	 Waren Sie seit Ihrer Entlassung nach der Schilddrüsen-Operation f ür mindestens eine Nacht im Krankenhaus? 					
		Nein				
		Ja 🗲	Bitte nenn der Klinik	en Sie nachfolgend jeweils Datum, Grund der Krankenhausaufnahme und Na	ne	
	A.	Datum		(Tag / Monat / Jahr)		
		Grund	-			
		Name	der Klinik			
	В.	Datum		(Tag / Monat / Jahr)	-	
		Grund	-			
		Name	der Klinik			
2.	War eine	en Sie s er Arztpro	eit Ihrer En axis?	ntlassung nach der Schilddrüsen-Operation bei einem niedergelassenen Arzt /	in	
		INEIN	Ditte	an Sie aankfelened invesile Datum. Cound and Easthrichtung dae Andre		
	u	Ja 🕇	(z. B. Hau	en Sie nachroigend jeweils Datum, Grund und Fachrichtung des Arztes sarzt, Orthopäde, Chirurg, Neurologe)		
	A.	Datum		(Tag / Monat / Jahr)		
		Grund				
		Fachri	chtung			
-	B.	Datum		(Tag / Monat / Jahr)	-	
		Grund				
		Fachri	chtung			
3.	Wu fes	ırde seit tgestellt'	Ihrer Entla: ?	ssung nach der Schilddrüsen-Operation eine neue chronische Erkrankung		
		Nein				

□ Ja → (bitte beschreiben)

HEDOS

HEDOS-Studie: Patienten-Fragebogen zum Verlauf

Patienten ID: «PatientID», Geschlecht: «Geschlecht», Geburtsjahr: «Geb.Jahr» (Zentrums-ID «CID»)

- Sind seit Ihrer Entlassung irgendwelche Beschwerden oder Krankheitszeichen aufgetreten? (z.B. Infektionen, Kopfschmerzen, Erbrechen etc., unabhängig von der Schilddrüsen-Operation)
 - Nein
 - □ Ja→ Bitte nennen Sie nachfolgend nähere Angaben:

Beschreibung der Beschwerden:	
Beginn:	(Tag / Monat / Jahr)
Intensität:	 Beschwerden sind gut tolerierbar Beschwerden behindern mich in meinem Alltag Ich kann nicht arbeiten oder meinen alltäglichen Aktivitäten nachgehen
Medikamentöse oder medizinische Behandlung dieser Beschwerden:	□ Nein □ Ja, (bitte beschreiben)
Aktueller Zustand:	Beschwerden bestehen nicht mehr Ende am (Tag / Monat / Jahr) Beschwerden dauern heute noch an
Beschreibung der Beschwerden:	
Beginn:	(Tag / Monat / Jahr)
Intensität:	 Beschwerden sind gut tolerierbar Beschwerden behindern mich in meinem Alltag Ich kann nicht arbeiten oder meinen alltäglichen Aktivitäten nachgehen
Medikamentöse oder medizinische Behandlung dieser Beschwerden:	□ Nein □ Ja, (bitte beschreiben)
Aktueller Zustand:	Beschwerden bestehen nicht mehr Ende am (Tag / Monat / Jahr) Beschwerden dauern heute noch an
Beschreibung der Beschwerden:	
Beginn:	(Tag / Monat / Jahr)
Intensität:	 Beschwerden sind gut tolerierbar Beschwerden behindern mich in meinem Alltag Ich kann nicht arbeiten oder meinen alltäglichen Aktivitäten nachgehen
Medikamentöse oder medizinische Behandlung dieser Beschwerden:	□ Nein □ Ja, (bitte beschreiben)
Aktueller Zustand:	 Beschwerden bestehen nicht mehr Ende am (Tag / Monat / Jahr) Beschwerden dauern heute noch an

EQ-5D-5L; Standardised measure of health-related quality of life developed by the EuroQol Group; version for Germany (deutsch)

Bitte kreuzen Sie unter jeder Überschrift DAS Kästchen an, das Ihre Gesundheit HEUTE am besten beschreibt.

BEWEGLICHKEIT / MOBILITÄT

Ich habe keine Probleme herumzugehen	
Ich habe leichte Probleme herumzugehen	
Ich habe mäßige Probleme herumzugehen	
Ich habe große Probleme herumzugehen	
Ich bin nicht in der Lage herumzugehen	

FÜR SICH SELBST SORGEN

Ich habe keine Probleme, mich selbst zu waschen oder anzuziehen	
Ich habe leichte Probleme, mich selbst zu waschen oder anzuziehen	
Ich habe mäßige Probleme, mich selbst zu waschen oder anzuziehen	
Ich habe große Probleme, mich selbst zu waschen oder anzuziehen	
Ich bin nicht in der Lage, mich selbst zu waschen oder anzuziehen	

ALLTÄGLICHE TÄTIGKEITEN (z.B. Arbeit, Studium, Hausarbeit, Familien- oder Freizeitaktivitäten)

Ich habe keine Probleme, meinen alltäglichen Tätigkeiten nachzugehen	
Ich habe leichte Probleme, meinen alltäglichen Tätigkeiten nachzugehen	
Ich habe mäßige Probleme, meinen alltäglichen Tätigkeiten nachzugehen	
Ich habe große Probleme, meinen alltäglichen Tätigkeiten nachzugehen	
Ich bin nicht in der Lage, meinen alltäglichen Tätigkeiten nachzugehen	
SCHMERZEN / KÖRPERLICHE BESCHWERDEN	
Ich habe keine Schmerzen oder Beschwerden	
Ich habe leichte Schmerzen oder Beschwerden	
Ich habe mäßige Schmerzen oder Beschwerden	
Ich habe starke Schmerzen oder Beschwerden	
Ich habe extreme Schmerzen oder Beschwerden	
ANGST / NIEDERGESCHLAGENHEIT	
Ich bin nicht ängstlich oder deprimiert	
Ich bin ein wenig ängstlich oder deprimiert	
Ich bin mäßig ängstlich oder deprimiert	
Ich bin sehr ängstlich oder deprimiert	
Ich bin extrem ängstlich oder deprimiert	

2

Germany (German) © 2009 EuroQol Group EQ-5D™ is a trade mark of the EuroQol Group

		Beste	
		Gesundheit, die Sie sich	
		vorstellen könner	n
•	Wir wollen herausfinden, wie gut oder schlecht Ihre		100
		±	95
•	Diese Skala ist mit Zahlen von 0 bis 100 versehen.		90
•	100 ist die beste Gesundheit, die Sie sich vorstellen können.	ŧ	85
	können.		80
•	Bitte kreuzen Sie den Punkt auf der Skala an, der Ihre		75
	Gesundheit HEUTE am besten beschreibt.		70
•	Jetzt tragen Sie bitte die Zahl, die Sie auf der Skala angekreuzt	+	65
	haben, in das Kastchen unten ein.		60
		+	55
	IHRE GESUNDHEIT HEUTE =	-	50
		±	45
			40
		+	35
			30
		+	25
			20
		+	15
			10
		+	5
			0
		Schlechteste Gesundheit die	
		Sie sich	
		vorstellen könne	n

3

Germany (German) © 2009 EuroQol Group EQ-5D™ is a trade mark of the EuroQol Group

Generalised Anxiety Disorder Scale-7 (GAD-7), version for Germany (deutsch)

Wie oft fühlten Sie sich im Verlauf der letzten 2 Wochen durch die folgenden Beschwerden beeinträchtigt?	Überhaupt nicht	An einzelnen Tagen	An mehr als der Hälfte der Tage	Beinahe jeden Tag	
a. Nervosität, Ängstlichkeit oder Anspannung		1		2	
	0	1	2	5	
b. Nicht in der Lage sein, Sorgen zu stoppen oder zu kontrollieren					
	0	1	2	3	
c. Übermäßige Sorgen bezüglich verschiedener Angelegenheiten					
	0	1	2	3	
d. Schwierigkeiten zu entspannen					
	0	1	2	3	
e. Rastlosigkeit, so dass Stillsitzen schwer fällt					
	0	1	2	3	
f. Schnelle Verärgerung oder Gereiztheit					
	0	1	2	3	
g. Gefühl der Angst, so als würde etwas Schlimmes passieren					
	0	1	2	3	
Gesamtwert	= Addition	ı	+	+	
der Spaltensummen					

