8.1 Adverse Events (AEs)

Is any untoward medical occurrence, unintended disease or injury, or untoward clinical signs (including abnormal laboratory findings) in subjects, users or other persons, in the context of a clinical investigation whether or not related to the IP. This definition includes events that are anticipated as well as unanticipated events and those occurring in the context of a clinical investigation related to the IP or the procedures involved. For users or other persons, this definition is restricted to events related to IPs.

Any surgery procedure or other intervention irrespective of its relation to the IP or the index thyroid surgery is an AE and has to be documented.

A newly diagnosed concomitant disease is also considered an AE.

All AEs occurring from enrolment until end of follow-up of each study patient will be documented by study site personnel in the e-CRF immediately after study site personnel's awareness of the event, and will subsequently be assessed by the sponsor and reported to authorities involved.

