8.2 Serious Adverse Events (SAEs)

A SAE is any untoward medical occurrence that

- led to death,
- Ied to serious deterioration in the health of the subject, that either resulted in
 - > a life-threatening illness or injury, or
 - > a permanent impairment of a body structure or a body function, or
 - > hospitalisation or prolongation of patient hospitalisation, or
 - medical or surgical intervention to prevent life-threatening illness or injury or permanent impairment to a body structure or a body function,
 - > a chronic disease,
- Ied to foetal distress, foetal death or a congenital abnormality or birth defect.

More than one of the above criteria can be applicable to each event.

These characteristics/consequences have to be considered at the time of the event. For example, regarding a life-threatening event, this refers to an event in which the subject was at risk of death at the time of the event. It does not refer to an event which hypothetically might have caused death if it were more severe.

NOTE:

The following overnight hospitalisations are not considered SAEs:

- Not urgent hospitalisation for
 - > a condition existing before signing consent, or
 - > a procedure required by the study protocol without serious deterioration in health.
- Elective inpatient hospitalisation (e.g. surgery) verifiably planned before signing consent.
- Any overnight hospital stay required only for diagnostic procedure (e.g. in a sleep laboratory).

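### The two contact items of the 1-month event questionnaire omit same-day hospital care, so procedures without complaints go unprompted and same-day treatment cannot be traced to a hospital (minor)

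*Protocol*

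**What the plan says.** EP3 (protocol section 4.2) is the safety of the device, measured by adverse events within 1 month of surgery. Sites document AEs directly up to hospital discharge (section 9.2.1). After that, the one scheduled assessment is by questionnaires mailed to the patient (Table 1, footnote 3; section 9.3.1).

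The event questionnaire (Appendix III) has four items:

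- Item 1 asks whether the patient spent "mindestens eine Nacht im Krankenhaus" since discharge, and collects date, reason and name of the clinic.
- Item 2 asks whether the patient was "bei einem niedergelassenen Arzt" or in a practice, and collects date, reason and specialty.
- Item 3 asks about "eine neue chronische Erkrankung".
- The open complaints item asks: "Sind seit Ihrer Entlassung irgendwelche Beschwerden oder Krankheitszeichen aufgetreten". It applies regardless of the thyroid operation and records description, onset, intensity, treatment (free text) and current state.

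The cover letter tells patients it is important to know whether they "beim Arzt oder im Krankenhaus waren", with no overnight or office-based limit.

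Section 8.1 states: "Any surgery procedure or other intervention irrespective of its relation to the IP or the index thyroid surgery is an AE and has to be" recorded. Section 8.2 lists, beside hospitalisation, the seriousness criterion "medical or surgical intervention to prevent life-threatening illness or injury or permanent impairment to a body structure or a body function". Neither carries an overnight condition.

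**The concern.** A patient who went to an emergency department, a hospital outpatient clinic or a day-case unit, and went home the same day, correctly answers no to items 1 and 2. The contact items therefore collect less than the cover letter says matters, and less than sections 8.1 and 8.2 define as reportable. Section 9.3.1 plans a telephone call only when no reply arrives, so a form returned with two negative answers triggers no further enquiry.

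At stake is the completeness of the post-discharge AE record for an invasive probe without market approval, and the site's ability to obtain hospital documents when an event may be serious.

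**Working it through.** The plan gives no expected post-discharge AE rate and no split of care by setting, so there is no figure to reproduce. The check is to take the kinds of post-discharge event and see which item prompts each one and whether a hospital name results.

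| Event after discharge | Item 1 | Item 2 | Open complaints item | Hospital name recorded? |
|---|---|---|---|---|
| Hospital stay of one night or more | yes | no | if symptomatic | yes |
| Visit to an office-based doctor | no | yes | if symptomatic | not applicable |
| Symptomatic event treated the same day at a hospital | no | no | yes | no |
| Same-day hospital procedure without complaints | no | no | no | no |

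Item 3 adds a prompt only where the event is a new chronic illness.

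**Fourth row.** Section 8.1 makes every procedure or intervention an AE, whether or not it relates to the device or the index operation. A same-day procedure without complaints, for example a planned one, meets that definition, and no item asks for it.

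**Third row.** The event is asked for, so it should reach the AE record. What is missing is the place of treatment: only item 1 collects the name of a clinic. Section 9.3.1 has the site ask the family doctor and/or the treating hospital for supporting documents once an event is suspected to be serious. For this row the form supplies no hospital to ask.

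**Recognising a possible SAE in the third row.** The complaints item grades intensity, but section 8.4.1 says that intensity and seriousness are independent. Whether a same-day intervention met the section 8.2 criterion must therefore be judged from the free-text treatment description alone, with no hospital contact flagged.

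**Illustration of scale, on assumed rates only.** Suppose 1% to 3% of the 1,470 patients have a wound-related event after discharge, and 20% to 50% of these are treated at a hospital without an overnight stay:

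- Lower end: 1,470 × 0.01 × 0.20 = 2.9
- Upper end: 1,470 × 0.03 × 0.50 = 22.1

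That is about 3 to 22 events outside items 1 and 2. This is not a count of events lost to EP3. They are symptomatic by assumption, so the complaints item asks for them. They are events for which the form gives no hospital name. Procedures without complaints are not in this range, and the documents give nothing from which to estimate them.

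**The case against.** The strongest reply is that AEs are defined by occurrence, not by where care was sought. On that view the open complaints item is the real AE question, and items 1 and 2 are supplementary prompts. It is a direct yes/no question, it applies in any care setting, it asks about treatment, and the first example it prints is infections, which is the device risk the protocol names. This stands, and it removes most of the worry about symptomatic wound events.

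There are also other routes. Section 8.1 obliges site staff to document any AE until the end of follow-up as soon as they learn of it. Section 8.4 requires SAE reports within 24 hours of awareness. Section 11.2 asks investigators to take all acceptable measures to retrieve outcomes. A patient who returns to the operating hospital may well be noticed. For suspected SAEs the family doctor can be contacted without a hospital name, and the site can ask the patient. These points stand too, but the awareness routes work least well for other hospitals, or for departments without study staff, and none of them puts the missing prompt on the form.

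The section 8.2 intervention criterion is narrow, so a same-day SAE with no complaint at all is a remote case. The cover letter is a general explanation to patients rather than a specification; it shows the intent but does not by itself create a contradiction.

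A reader might infer that EP3 under-counts AEs in general, that the device will look safer than it is, or that a large share of wound events, perhaps half, would be missed. The documents do not support this. It would require the complaints item to capture few or none of these events, and nothing in the protocol suggests so.

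**Conclusion.** The point holds in a limited form and is minor. Items 1 and 2 leave out same-day hospital care. Two consequences follow from the text alone: same-day hospital procedures without complaints are AEs under section 8.1 that no item prompts, and symptomatic events treated the same day at a hospital are recorded without the hospital name that section 9.3.1 would use.

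The effect is some incomplete AE capture and SAE tracing. Its size cannot be derived from the documents, and the 3 to 22 events above rest entirely on assumed rates and concern traceability only. No bias in the reported safety of the device is shown. EP3 is analysed descriptively (section 12.1.3), so no test depends on it, and EP1, EP2 and the sample size are untouched.

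The conclusion assumes that patients read the two contact items literally and that most patients with symptoms answer the complaints item as asked.

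**What to change.** Reword item 1 to cover any hospital contact since discharge: *stationär oder ambulant (z. B. Notaufnahme, Ambulanz, ambulanter Eingriff)*. Add a tick box for overnight stay, yes or no, so that hospitalisation SAEs can still be identified. Keep the fields for date, reason and name of the clinic. Use the same wording in the telephone contact of patients who do not reply.

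This prompts the same-day procedures that are now unprompted, supplies the hospital name for the document request, and brings the form into line with its own cover letter. The cost is an edit to the form and the e-CRF, an ethics notification, and a few more site queries for hospital documents. No analysis changes.
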